5.3.3 Other Effectiveness Analyses

The following outcomes will be summarized descriptively at each scheduled visit based on the available data:

- IOP, IOP change, and IOP percent change from baseline
- Number of glaucoma medications and change in the number of glaucoma medications from baseline

5.4 Safety Analyses

Adverse events (AEs) will be classified as intraoperative or postoperative. The AEs will be summarized by counts and percentages. They will also be summarized by severity (mild, moderate, severe) and relationship to the study device and implantation procedure.

Additionally, the frequency and percentage of the serious adverse events will be presented. The summaries of the adverse events will be separated by ocular and non-ocular events.

6.0 ADVERSE EVENTS

6.1 Adverse Event Definitions

An adverse event (AE) is any untoward medical occurrence, unintended disease or injury, or untoward clinical signs in subjects, users or other persons, whether or not related to the microstent or delivery system. Conditions or diseases that are chronic but stable (unchanged) should not be recorded as an AE. Changes in a chronic condition or disease that are consistent with natural disease progression are NOT adverse events and also should not be recorded. Events that occur during the screening period should not be recorded. AEs should be recorded starting with the Operative Visit.

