6.8.1 Anticipated Adverse Events

Anticipated AEs associated with glaucoma surgical procedures that might reasonably be expected to occur in this study are listed below. These specific examples of anticipated AEs include, but are not limited to:

Intraoperative Adverse Events

- Choroidal hemorrhage or effusion
- Corneal abrasion
- Corneal edema
- Cyclodialysis cleft
- Hyphema obscuring the surgeon's view
- Inadvertent perforation of the sclera
- Iridodialysis
- Lens / capsular bag damage (crystalline or IOL)
- Microstent malposition
- Significant iris injury or trauma
- Vitreous loss
- Zonular dialysis

Postoperative adverse events include

- Angle closure
- Angle recession
- Anterior chamber cell or flare requiring either an increase in the standard postoperative steroid regimen or re-initiation of steroid use following completion of the standard postoperative steroid regimen.
- Aqueous misdirection
- Atrophy, phthisis
- Best-corrected visual acuity loss of 2 lines (10 letters) or more compared to baseline on the ETDRS chart measured before or at 1-month postoperative
- Best-corrected visual acuity loss of 2 lines (10 letters) or more compared to baseline on the ETDRS chart measured after 1-month postoperative
- Blebitis
- Choroidal detachment
- Choroidal hemorrhage or effusion (detachment with at least a partially hemorrhagic component that obstructs or causes pain, including both peripheral and "kissing" choroidal detachments) lasting 30 days or less
- Choroidal hemorrhage or effusion (detachment with at least a partially hemorrhagic component that obstructs or causes pain, including both peripheral and "kissing" choroidal detachments) lasting longer than 30 days
- Chronic anterior uveitis defined as inflammation of grade 1+ or worse persisting for more than 90 days postoperatively or that recurs less than 90 days after discontinuing standard medication regimen
- Chronic pain in the study eye onset ³ 3-months postoperative
- Corneal decompensation

- Corneal edema persisting > 30 days (mild to moderate) or severe corneal edema ≥ 1 day.
- Corneal opacification
- Descemet's membrane detachment
- Device migration (dislodgement or movement)
- Device obstruction
- Elevated mean IOP ≥ 10 mmHg than the qualifying baseline mean IOP onset before or at 1-month postoperative
- Elevated mean IOP ≥ 10 mmHg than the qualifying baseline mean IOP onset after 1-month postoperative
- Endophthalmitis

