- Flat anterior chamber with lens/cornea touch or shallow anterior chamber with peripheral iridocorneal apposition
- Hyphema ≥ 2 mm in height (layered) at any time
- Hyphema present or arising > 30 days postoperative
- Hypotony (defined as IOP < 6 mmHg) onset before 1-month postoperative
- Hypotony (defined as IOP < 6 mmHg) onset at or after 1-month postoperative
- Implant corneal touch
- Implant-iris touch associated with intraocular inflammation, pigment dispersion, or other sequelae
- Inadvertent bleb
- Increase in vertical C/D ratio of ≥ 0.3 units from screening on fundus examination
- Iris prolapse/wound incarceration
- Maculopathy including hypotonic maculopathy
- Persistent diplopia
- Pupil block
- Retinal complications (e.g., flap tears, retinal break, retinal detachment, age related macular degeneration, diabetic retinopathy, macular edema, epiretinal membrane, central serous retinopathy, or proliferative vitreoretinopathy)
- Scleral ectasia
- Surgical re-intervention in the study eye (other than paracentesis to relieve pressure within the 1 week visit)
- Toxic anterior segment syndrome (TASS)
- Vitreous haze
- Vitreous hemorrhage
- Vitritis
- Worsening of 2-points (from screening) to "severe" on the slit lamp examination findings (other than cells and flare) onset at or after 3-months postoperative not associated with a pre-existing condition
- Worsening of lens opacities (defined as a 2.0 or more score change on at least one category of the LOCS III grading system, at 2 or more consecutive visits)
- Worsening of visual field (mean deviation worsening by 3.0 dB or more, confirmed by 2 repeat measurements)
- Wound dehiscence (persistent aqueous leak or fistula formation)

For any adverse event that may be due to incorrect device positioning (i.e. vitreous hemorrhage, hyphema, hypotony), gonioscopy should be performed to assess the device position. If the position cannot be adequately evaluated by gonioscopy, ultrasound biomicroscopy (UBM) should be performed.

For slit lamp examination, gonioscopy and fundus findings for which there is no grading scale, any finding considered by the study investigator to be marked or severe, i.e., clinically significant, should be recorded as an Adverse Event.

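### Sections 6.1 and 6.8.1 do not settle whether glaucomatous field and disc worsening is recorded as an adverse event, and no other planned output would show it

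*Combined protocol and SAP*

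**What the plan says.** Section 6.1 (Adverse Event Definitions) sets an exclusion: "Changes in a chronic condition or disease that are consistent with natural disease progression are NOT adverse events and also should not be recorded".

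Section 6.8.1 (Anticipated Adverse Events) lists two measures of glaucomatous damage among the postoperative events: "Worsening of visual field (mean deviation worsening by 3.0 dB or more, confirmed by 2 repeat measurements") and "Increase in vertical C/D ratio of ≥ 0.3 units from screening on fundus examination". Neither has an exception by cause. The slit-lamp item does have one; it is limited to worsening with "onset at or after 3-months postoperative not associated with a pre-existing condition".

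The last paragraph of 6.8.1 turns to slit-lamp, gonioscopy and fundus findings that have no grading scale. It says that "any finding considered by the study investigator to be marked or severe, i.e., clinically significant, should be recorded as an Adverse Event". It too makes no exception for progression.

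Section 6.2 records adverse events whether or not they are ascribed to the device. Section 6.5 makes attribution to underlying illness a ground for the category of not related. Section 5.4 summarises adverse events by counts and percentages, severity and relationship. Section 5.3.3 adds visit summaries of IOP and number of medications. Section 5.1 makes subject listings optional.

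**The concern.** Section 3.2 requires glaucomatous optic nerve pathology and visual field defects at entry, with MD of -3 dB or worse. A later fall in MD or a larger cup is how progression of that disease would appear. An investigator who relies on 6.1 can therefore leave such a change unrecorded. Another who relies on 6.8.1 can record the same change. Both are following the protocol.

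The public text describes no control group, so whether a change is natural rests on each investigator's judgment. What is at stake is the readability of the safety table: a reader of the 5.4 summary could not tell how many subjects crossed the protocol's own thresholds for field or disc worsening.

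**Working it through.** The documents give no expected event rate, so there is no figure to reproduce. The check is mainly a comparison of the passages.

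**1. Does 6.8.1 carry a progression exception?** The postoperative list has 46 items. One of them, the slit-lamp item, excludes an association with a pre-existing condition. The MD and C/D items do not.

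**2. Does any section set precedence?**

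| Section | What it does | Does it settle the question? |
|---|---|---|
| 6.1 | Excludes changes consistent with natural progression | Does not mention the 6.8.1 thresholds |
| 6.2 | Records adverse events regardless of attribution | No: it presupposes that the change is an adverse event |
| 6.4 | Classes adverse events as anticipated or not | No: same reason |
| 6.5 | Lets underlying illness be a reason for not related | Suggests such events are recorded and then attributed, but does not say so |
| 6.8.1, list | Gives thresholds for MD and C/D | Does not say that a threshold marks change beyond progression |
| 6.8.1, last paragraph | Says marked or severe ungraded findings should be recorded | Opposes 6.1 within its scope |

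**3. Where is the conflict direct?** Take a marked fundus change with no grading scale that the investigator judges to be progression. Section 6.1 says not to record it; the last paragraph of 6.8.1 says to record it. MD is a perimetry result and lies outside that paragraph. C/D has a numeric threshold of its own and is at best doubtfully inside. For these two the text is open, not contradictory.

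**4. How far can reported rates differ?** Let q be the proportion of subjects who meet a threshold and f the share of those judged consistent with progression. A site that follows the 6.8.1 thresholds reports q. A site that follows 6.1 reports q(1 - f). With f assumed anywhere from 0 to 1, the reported rate for identical data runs from q down to 0. Neither q nor f is given.

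**5. Are the findings trivial?** With entry MD at -3 dB or worse, a loss of 3.0 dB gives -3 - 3.0 = -6 dB or worse.

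**6. Would another output show them?** Section 5.3.3 covers IOP and medications only. No summary of field or C/D is planned, and listings are optional. The 5.4 adverse event summary is the only planned output that would show them.

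**7. Can MD loss be confirmed at scheduled visits?** The schedule in section 4.0 places postoperative fields at 2, 3, 6, 9 and 12 months. Taking the two repeats to be later scheduled fields:

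| Loss first seen at | Later scheduled fields | Two repeats possible? |
|---|---|---|
| 2 months | 4 | Yes |
| 3 months | 3 | Yes |
| 6 months | 2 | Yes |
| 9 months | 1 | No |
| 12 months | 0 | No |

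A table of confirmed loss alone, built from scheduled visits, would miss late loss.

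**The case against.** The strongest reply is that the sections can be harmonised. Section 6.1 decides what is an adverse event. The 6.8.1 list, introduced as events associated with glaucoma surgery, only classes such events as expected under 6.4. Alternatively, a confirmed 3.0 dB loss or a 0.3 C/D change may be meant to mark change beyond natural progression. Both readings are reasonable for MD and C/D, so a reader who infers a flat contradiction on those items goes further than the text. But the documents state neither reading, and the two lead to different recording. The ambiguity stands.

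The last paragraph of 6.8.1 is also narrower than it may look. It covers only findings without a grading scale, it says should rather than must, and the scales in Appendix 2 are not in the public text, so the affected fundus findings cannot be listed here. Within its scope the conflict with 6.1 remains.

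A reader might infer three further things that the documents do not support:

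- **That any error is toward too few events.** If 6.1 governs, a site that records progression reports too many. The direction depends on the rule that is missing.
- **That an unrecorded finding can never become a serious adverse event.** Section 6.1.2 separately says that sight-threatening events should be reported as serious, and its list is not exhaustive.
- **That the elevated-IOP items are equally exposed.** Section 5.3.3 already summarises IOP at each visit, and it is strained to call a rise of 10 mmHg or more by 1 month after surgery natural progression.

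**Conclusion.** The point holds in limited form. There is a direct conflict for marked or severe ungraded findings judged to be progression, and an unresolved ambiguity for the MD and C/D thresholds. Sites that all comply can report different rates for the same findings, and no other planned output would reveal it. The size in events cannot be derived from the documents, and neither can the direction.

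The conclusion assumes that some threshold-level changes will be judged consistent with progression. That is plausible where every subject enters with glaucomatous disc and field damage, but the documents do not quantify it. The field and disc examinations are carried out whatever is entered as an adverse event, so the loss is in reporting, not in data. The primary endpoint is unaffected. The point is worth correcting because the remedy is cheap, but it does not threaten the main result.

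**What to change.** 1. **State precedence in 6.1.** Add that the progression exception does not apply to a finding that meets the MD or C/D threshold in 6.8.1, or that the last paragraph of 6.8.1 says should be recorded. Such findings are recorded whatever their presumed cause, and attribution is entered under 6.5. Stating instead that 6.1 governs would also end the inconsistency, but the table in item 2 would then be the only place to see how many subjects worsened.

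2. **Add a descriptive table to 5.4**, derived from visit data and independent of adverse event entry. It gives the Safety Population subjects who meet the C/D threshold (against screening, as 6.8.1 states) and the MD threshold (against the 5.1 baseline). Show confirmed and unconfirmed MD loss separately, since loss first seen at 9 or 12 months cannot be confirmed twice at scheduled visits. Report the number examined beside each count: subjects who do not receive the microstent may be followed for only 1 month, before the first scheduled postoperative field and fundus examinations at 2 months.

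**Cost.** One sentence, one table and a little programming, all from examinations already scheduled. Reported adverse event rates may rise with events due to glaucoma itself; the 5.4 summary by relationship keeps those apart from device-related events.

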3.3 Screening Exclusion Criteria

Excluded from the study will be individuals with the following characteristics. Unless specified otherwise, all ocular criteria refer to the study eye only.

- Secondary glaucoma other than pseudoexfoliative and pigmentary (e.g., neovascular, uveitic, traumatic, steroid induced, lens induced, or glaucoma associated with increased episcleral venous pressure)
- Diagnosis of acute angle closure, chronic angle closure, or congenital, malignant, or developmental glaucoma
- Central visual field depression within 5 degrees of fixation with sensitivity < 15 dB in both hemifields on the numerical/dB plot
- Pre-perimetric glaucoma
- Ocular hypertension
- Shallow or flat anterior chamber
- Presence of peripheral anterior synechiae or iris processes obscuring angle visualization
- Central corneal thickness greater than 620 or less than 480 microns
- History of complicated intraocular surgery (e.g., vitreous in anterior chamber, zonular dehiscence)
- History of failed Schlemm's canal procedure (including but not limited to Glaukos iStent, Ellex ABiC, SightSciences Trab360, or New World Medical Kahook Dual Blade)
- Epithelial or fibrous downgrowth

- Aphakia
- Currently implanted anterior chamber IOL
- Retinal laser within 90 days prior to screening
- A need for additional ocular surgery (e.g., cataract surgery) or retinal laser procedure within the 12-month postoperative period
- Proliferative diabetic retinopathy (PDR)
- History of retinal detachment repair with silicone oil or scleral buckling procedure
- Corneal dystrophy (e.g., Fuch's Dystrophy, defined as > 12 confluent endothelial guttae) or corneal opacity
- Previous corneal surgery, including lamellar or penetrating keratoplasty, LASIK or PRK
- Fellow eye best-corrected visual acuity (BCVA) worse than 20/200
- Inability to complete a reliable Humphrey-Zeiss 24-2 SITA Std visual field on the study eye (fixation losses, false positive, and false negative errors should not be greater than 33%)
- Fellow eye visual field mean deviation worse than -18.00 dB
- Exudative age-related macular degeneration (AMD)
- History of intraocular inflammation or infection within 90 days prior to screening
- Use of oral hypotensive medication (e.g., acetazolamide) for glaucoma treatment
- Uncontrolled systemic disease that in the opinion of the Investigator would put the subject's health at risk and/or prevent the subject from completing all study visits

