- Unable to suspend or temporarily discontinue use of blood thinners (e.g., warfarin, heparin, aspirin, etc.) in accordance with surgeon's standard instructions
- Pregnant or nursing women; or women of child bearing age not using medically acceptable birth control
- Current participation or participation within the past 30 calendar days in another investigational drug or device clinical trial
- Known or suspected allergy to nickel

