3.6 Enrollment

Patients who sign the informed consent form (ICF) are considered enrolled. Study specific exams should be initiated only after ICF is obtained.

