4.0 CLINICAL FOLLOW-UP SCHEDULE

All subjects will be scheduled to return for follow-up examinations at defined intervals through 12 months. **Table 5** shows the schedule of events and procedures at each protocol-required visit.

SCHEDULE OF VISITS

| Procedure | Screening ¹ | Baseline (30 days from Scr) | Surgery (30 days from BL) | 1D Postop (+/- 2D) | 7D Postop (+/- 2D) | 1M Postop (30+/- 7D) | 2M Postop (60+/- 10D) | 3M Postop (90+/- 14D) | 6M Postop (183+/- 14D) | 9M Postop (274+/- 30D) | 12M Postop (365+/- 45D) |
|---|------------------------|--------------------------------|------------------------------|-----------------------|-----------------------|-------------------------|--------------------------|--------------------------|---------------------------|---------------------------|----------------------------|
| Informed Consent | X | | | | | | | | | | |
| Medical History Ophthalmic and Non-Ophthalmic | X | | | | | | | | | | |
| Medication Assessment | X | X | X | X | X | X | X | X | X | X | X |
| Manifest Refraction | X | X | | X | X | X | X | X | X | X | X |
| BCVA - Snellen | X | | | | | | | | | | |
| Visual Acuity-Pinhole | | | X | | | | | | | | |
| BCVA - ETDRS | | X | | | X | X | X | X | X | X | X |
| Intraocular Pressure Goldmann Applanation Tonometry | | X | | X | X | X | X | X | X | X | X |
| Diurnal Intraocular Pressure Goldmann Applanation Tonometry | | | X ³ | | | | | | | | X ³ |
| Intraocular Pressure 2 to 6 hours after surgery | | | | X ⁴ | | | | | | | |
| Pachymetry CCT | X | | | | | X | X | X | X | X | X |
| Gonioscopy | X | | | | | X | X | X | X | X | X |
| Slit Lamp Exam | X | X | | X | X | X | X | X | X | X | X |
| Lenticular Opacity Grading | X ⁵ | | | | | X ⁵ | | | X ⁵ | | X ⁵ |
| Visual Field Humphrey 24-2 SITA Standard | X | | | | | | X | X | X | X | X |
| Fundus Exam/Disc Evaluation | X | | | | | | X | X | X | X | X |
| Optic Disc Photography | X | | | | | | | | | | X |
| Subject Questionnaire | X | | | | | | | X | | | X |
| Hydrus Implantation | | | | X ⁶ | | | | | | | |
| Adverse Event Assessment | | | | X | X | X | X | X | X | X | X |

¹ At the Screening Visit, all assessments will be performed for both eyes.

² At the Baseline Visit, both eyes may be evaluated if eligibility confirmed after all Screening procedures completed.

³ Daytime-Diurnal IOP measurements will be performed 3 times at 8:00 AM (± 1 hour), 12:00 PM (± 1 hour), and 4:00 PM (± 1 hour).

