5.0 STATISTICAL METHODS

5.1 General Data Handling

Descriptive statistics on continuous variables will include mean, standard deviation, median, and range. Confidence intervals will be included for selected endpoints. Categorical variables will be summarized using frequency counts and percentages. A confidence level of 95% will be used for the confidence intervals. Statistical testing will be two-sided with a significance level of 0.05 or one-sided with a significance level of 0.025 unless specified otherwise. Data listings of individual subject data may be provided.

The baseline values are those that are obtained at the closest visit prior to the surgery. The arithmetic difference between the baseline and the postoperative visit are defined as follows:

Change from baseline = postoperative value – baseline value

Percent change from baseline = change from baseline ÷ baseline X 100.

The Safety Population includes all subjects for whom a Hydrus microstent was implanted or implantation was attempted.

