6.2 Adverse Event Assessment and Documentation

All subjects who undergo attempted implantation of the Hydrus will be evaluated for adverse events. All adverse events, regardless of severity and whether or not they are ascribed to the Hydrus implant or delivery system, will be recorded using standard medical terminology. All events for the study eye, fellow eye, and non-ocular are to be recorded.

All adverse events will be evaluated beginning with onset, and evaluation will continue until resolution is noted, or until the investigator determines that the subject's condition is stable.

The investigator will take appropriate and necessary therapeutic measures required for resolution of the adverse event. Any medication necessary for the treatment of an adverse event must be recorded.

All AEs will be characterized by the following criteria:

- Event term
- Severity
- Expectedness
- Relationship to study device or procedure
- Outcome
- Treatment or action taken.

Whenever possible, recognized medical terms should be used when recording AEs. Colloquialisms and/or abbreviations should not be used. Only one medical concept, preferably a diagnosis instead of individual symptoms, should be recorded as the event.

If more than one distinct adverse event occurs, each event should be recorded separately.

However, if known at the time of reporting, a diagnosis (i.e., disease or syndrome) should be recorded rather than individual signs and symptoms (e.g., record congestive heart failure rather than dyspnea, rales, and cyanosis). However, if a constellation of signs and/or symptoms cannot be medically characterized as a single diagnosis or syndrome at the time of reporting, each individual event should be recorded as a separate AE. A diagnosis that is subsequently established should be reported as follow-up information. However, signs and symptoms that are considered unrelated to an encountered syndrome or disease should be recorded as individual AEs (e.g., if congestive heart failure and severe headache are observed at the same time, each event should be recorded as an individual AE).

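### Events with onset between consent and the Operative Visit, including serious ones and any that follow a blood-thinner suspension made for the study surgery, are not recorded

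*Combined protocol and SAP*

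**What the plan says.** Enrollment comes first. Section 3.6 reads: "Patients who sign the informed consent form (ICF) are considered enrolled". The schedule in section 4.0 places consent at Screening and heads the next two columns "Baseline (30 days from Scr) | Surgery (30 days from BL".

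Recording of events comes later. Section 6.1 reads: "Events that occur during the screening period should not be recorded. AEs should be recorded starting with the Operative Visit". Section 6.2 sets the group to be assessed: "All subjects who undergo attempted implantation of the Hydrus will be evaluated for adverse events". Section 5.1 sets the analysis group to match: "The Safety Population includes all subjects for whom a Hydrus microstent was implanted or implantation was attempted". Section 5.4 sorts adverse events into intraoperative and postoperative, with no earlier class.

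Blood thinners appear once, among the exclusions in section 3.3: "Unable to suspend or temporarily discontinue use of blood thinners (e.g., warfarin, heparin, aspirin, etc.) in accordance with surgeon's standard instructions". The plan does not say when a suspension would start, how long it would last or when the drug would be resumed.

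**The concern.** Starting the record at the procedure is easy to defend when nothing about a subject's care changes beforehand. Here something may change. A subject on a blood thinner is eligible only if able to stop it under the surgeon's usual instructions. Where those instructions call for stopping before the day of surgery, the unrecorded interval contains a change in care made for the study operation.

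Suppose such a subject has a thromboembolic event two days before surgery. Section 6.1 says not to record it. If the operation is then cancelled, the subject also never enters the group whose safety is assessed or analysed. The safety record would be silent on the event, even if it were fatal.

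**Working it through.** No formula applies beyond the length of the gap, and the plan states no figure to reproduce. The check is whether any provision captures an event with onset between consent and the Operative Visit.

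**Length of the gap.** The inputs are the two column headings in section 4.0: 30 days from Screening to Baseline and 30 days from Baseline to Surgery. 30 + 30 = 60 days. This is an upper limit if each figure is a maximum; the schedule gives no tolerance for either. The part of it that a subject would spend off a blood thinner cannot be derived.

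**Does a narrow reading of the screening period help?** No. The first sentence of the rule in 6.1 might be confined to the time before Baseline, but the second sets the start at the Operative Visit and so covers Baseline to Surgery as well.

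**Provisions that might close the gap:**

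| Provision | Does it capture a pre-operative event? |
|---|---|
| 6.1.1, serious adverse events | No. A serious event is an adverse event that meets further criteria, so it inherits the 6.1 start. |
| 6.8, reporting of serious events to the sponsor | No. It applies to events already classed as serious under 6.1.1. |
| 6.1.3, unanticipated adverse device effects | No. The definition requires a link to the device, which has not yet been used. |
| 6.2, assessment of events | No. It covers subjects with attempted implantation. From the Operative Visit it takes in every event in them, whatever the cause, including non-ocular events. |
| 4.0, footnote 6, follow-up of subjects without an implant | No. It concerns subjects who go to surgery and do not receive the microstent, not those whose surgery is cancelled. |
| 4.0, Medication Assessment before surgery | No. It documents drugs, not events. |
| 5.1 and 5.2, analysis populations | No. Each requires implantation, attempted implantation or implantation surgery. |
| 5.4, classes of event | No. There is no pre-operative class. |

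The Adverse Event Assessment row of the schedule was left out of this check, because the columns of the table as extracted appear to have shifted.

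**Two cases side by side.** A subject suspends a blood thinner and has an event. If onset is on or after the day of the Operative Visit and implantation is attempted, 6.1 and 6.2 together capture it regardless of cause. If onset is the day before, 6.1 excludes it. The difference comes only from the start date.

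**The case against.** The rule is explicit and consistent. Sections 5.1, 5.4, 6.1 and 6.2 all look from the operation onward, which suits a trial whose safety question concerns a device and its implantation. A separate listing would leave every planned device or procedure rate as it is, so no planned rate is shown to be biased. That stands, and it limits the weight of the point. It does not remove the gap: the plan accepts all-cause, non-ocular events once recording begins, yet gives no route for a serious event in an enrolled subject before then.

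Several stronger readings are tempting, and the documents do not support them.

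- **That the protocol requires a suspension step.** Section 3.3 tests ability and defers to the surgeon's own practice. No suspension is scheduled, and stopping before the operative day is a reasonable inference, not stated text.
- **That all harm from a suspension is lost.** Section 6.2 captures events with onset at or after the Operative Visit whatever their cause. Only earlier onset is lost.
- **That no pre-operative record of the eye exists, so earlier inflammation will be blamed on the device.** The schedule as extracted shows slit lamp examination at Screening and Baseline and medication assessment up to surgery. Section 6.5 also lets the investigator attribute an event to an underlying illness. Misattribution could arise only for an episode that these miss.
- **That the gap as a share of study time measures the loss.** It measures calendar time, not events, and the documents give neither the number of blood-thinner users nor an event rate.

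The exclusions that look back from Screening, such as "History of intraocular inflammation or infection within 90 days prior to screening", raise a question of eligibility timing. That is a separate matter and lends this point no support.

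**Conclusion.** The point holds in a narrow form. Adverse events and serious adverse events with onset after consent and before the Operative Visit are excluded by a stated rule, over a gap of up to about 60 days if each 30-day window is a maximum. A subject harmed in that interval whose surgery is cancelled is also outside the groups defined in 5.1 and 6.2. Harm from suspending a blood thinner for the study surgery falls in the gap if its onset precedes the visit. This last step assumes that some surgeons' instructions call for stopping before the operative day.

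The number of events lost is unknown and may be small. The consequence is an incomplete safety record for enrolled subjects, not a wrong device or procedure rate. The change is worth making because the missing events could be serious and the cost is low.

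**What to change.** Amend section 6.1 so that recording starts at consent for, at minimum:

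- all serious adverse events;
- all study-eye events;
- any event following a pre-operative medication suspension made for the study surgery.

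Add a pre-operative class in section 5.4 and present it as a separate listing over all enrolled subjects, including those whose surgery is cancelled. Keep the intraoperative and postoperative summaries on their present population and start, so those rates do not change.

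Reconcile sections 3.3, 3.6, 6.1 and 6.2, so that the point of enrollment, the start of recording and the group assessed agree, and so that 6.2 no longer limits assessment to subjects with attempted implantation. No change to the suspension instructions themselves is proposed.

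The cost is an edit to 6.1 with matching edits elsewhere, one extra listing and a few more adverse event forms. Sites already see subjects at Baseline and Surgery.
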